6.0 STUDY PROCEDURES

6.1 Screening Procedures (Within 28 days of Baseline)

Assessments performed exclusively to determine eligibility for this study will be done only after obtaining informed consent. Assessments performed for clinical indications (not exclusively to determine study eligibility) may be used for baseline values even if the studies were done before informed consent was obtained.

All screening procedures must be performed within 28 days prior to registration unless otherwise stated. The screening procedures include:

6.1.1 Informed Consent

Informed consent will be obtained in accordance with the Institutional Review Board (IRB) policies and procedures as described in the IRB application. For non-English speaking patients, an interpreter will be used.

6.1.2 Medical history

Relevant medical history, including history of current disease and information regarding underlying diseases (Medical record review)

6.1.3 Demographics

Age, gender, race, ethnicity

Patients may be offered the Inclusive Demographics Questionnaire, which is a standard, non-study-specific document, available on the [IRB Intranet](#). Study team to record responses in the subject's OnCore record. Completion is voluntary; patients may decline to complete the Inclusive Demographics Questionnaire.

6.1.4 Pregnancy status

Pregnancy status will be confirmed with patient and via medical record review.

6.1.5 Godin-Shephard Leisure-Time Physical Activity Questionnaire

For non-English speaking patients, an interpreter will be used for the questionnaire.

6.1.6 Physical Activity Readiness Questionnaire (PAR-Q)

Patients who answer no to all questions on the PAR-Q will not require physician clearance. Any patients who answer yes to a question may be cleared by either a) their treating/referring oncologist or b) one of the study physicians following an in-person visit or phone call with chart review.

For non-English speaking patients, an interpreter will be used for the questionnaire.

6.1.7 Physical Activity assessment

Ambulatory status, ability to complete functional assessments including 6-minute walk test, hand grip strength, short performance physical battery and performance metrics.

6.1.8 Review subject eligibility criteria**6.2 Baseline Procedures (within 14 days of first PREHAB session)**

All baseline procedures will occur after the patient is deemed to be eligible by review of the eligibility criteria.

6.2.1 Physical Evaluation

- Vitals (Height, Weight, Body Mass Index (BMI))
- Six-minute walk test
- Hand grip strength
- Physical performance metrics
 - Strength is measured in reps within 60 seconds of leg press, bicep curls, heel raises, plank holds and lateral pull downs.
 - Functional testing includes the sit to stand test.
 - Balance testing includes static standing balance with the eyes open and closed on firm and foam surfaces. Balance is rated as poor, fair, good, or excellent.
- Short performance physical battery

6.2.2 Questionnaires

- Patient-Reported Outcomes Measurement Information System (PROMIS-29)
- Patient-Reported Outcomes Measurement Information System Cancer Function (PROMIS Cancer 3D Function)

For non-English speaking patients, an interpreter will be used for the questionnaires.

6.2.3 SOC Abdomen CT scan

- Document date of closest SOC Abdomen CT scan (ok if occurred prior to consent or greater than 14 days prior to first PREHAB session)

6.2.4 Review of SOC Lab Results

- Participants are anticipated to be undergoing neoadjuvant therapies concurrently with study participation. These therapies may impact the participants circulating cytokines, thus rendering them ineligible to participate in physical activity.

Prior to each PREHAB session exercise physiologist or personal trainer will check the participants' medical records for the most recent SOC lab results. To participate all 3 thresholds must be met:

- absolute neutrophils >0.5 $1000/UL$
- platelets > 50 $1000/UL$
- hemoglobin >8 g/dl

If one or more of these thresholds are not met the PI will be notified and the participant will be unable to participate in the exercise session. Sessions will resume when all lab values have reached the required thresholds or at the PI's discretion.

These thresholds were determined by the cancer rehabilitation physiatrists and referring pancreatic oncologists and are in line with other cancer activity recommendations^{19,20}.

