5.3 Standard of Care (SOC) Procedures

As SOC, patients will undergo Computed Tomography (CT) scans periodically throughout their pancreatic cancer diagnosis and treatment. This study will review SOC Abdomen CT scans undertaken closest to both the Baseline and 3 month follow up visit.

Patients will also undergo SOC labs periodically throughout their pancreatic cancer diagnosis and treatment. This study will review SOC labs undertaken closest to each PREHAB session to determine safe physical activity participation.

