6.3.2 Post-Intervention Evaluation (Within 14 days following the last PREHAB session)

Can be on the same day as the last PREHAB session

- Vitals (Weight, BMI)
- Six-minute walk test
- Hand grip strength
- Physical performance metrics
- Short performance physical battery
- Unanticipated Problem review
- PROMIS-29 (for non-English speaking patients, an interpreter will be used for the questionnaire)
- PROMIS Cancer 3D Function Profile (for non-English speaking patients, an interpreter will be used for the questionnaire)
- Patient Global Impression of Change (Only those participants who used the Online Pain portal)
- Continuous activity monitoring (Fitbit)

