6.5 Time and Events Table

	Screening (Within 28 days of Baseline)	Baseline (Within 14 days of first PREHAB session)	Week 1 – Week 6¹	Post-Intervention Evaluation (Within 14 days of last PREHAB session)	3 Month Follow-Up (± 14 days)
Informed Consent	X				
Confirm Eligibility	X				
Medical History	X				
Demographics	X				
Pregnancy status ²	X				
Godin Leisure-Time Exercise Questionnaire	X				
PAR-Q	X				
Physical Activity Assessment	X				
Vitals (Height, Weight, BMI) ³		X		X	X
Six Minute Walk Test		X		X	X
Hand Grip Strength		X		X	X
Physical Performance Metrics		X		X	X
Short Performance Physical Battery		X		X	X
Unanticipated Problem review			X	X	X
PROMIS-29		X		X	X
PROMIS Cancer 3D Function Profile		X		X	X
SOC Abdomen CT Scan ⁴		X			X
SOC Lab Test Review		X	X ⁵		
Fitbit activity monitoring ⁶		X	X	X	X
Dietitian referral ⁷		X			
Online Pain platform ⁸ Training		X			
Online Pain platform use ⁸			X		
Online Pain platform compliance			X ⁹		
3 x Weekly 1HR PREHAB session			X		
Patient Global Impression of Change ¹⁰				X	
Healthcare Utilization Assessment					X

BMI: Body Mass Index, CT: Computed Tomography, PAR-Q: Physical Activity Readiness Questionnaire

1. Up to 3 missed sessions will be made up in a 7th week
2. Pregnancy status confirmed with patient and via medical record review

3. Height will only be collected at Baseline
4. CT scans completed closest to baseline and 3-month follow-up will be used, even if they occurred outside of the relevant visit window.
5. SOC labs will be reviewed prior to each PREHAB session
6. Fitbit use is only required by those who met eligibility criteria 4.1.9 and do not meet exclusion criteria 4.2.3.
7. Only patients not previously referred to a Dietitian will be referred by the study team
8. Online Pain platform training and use is only required for those who met eligibility criteria 4.1.9 (First 8 participants only)
9. Online Pain platform compliance will be self-reported every 2 weeks (First 8 participants only)
10. Only completed by the participants who used the Online Pain Portal

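### The blood-count thresholds guard supervised sessions only; no count check is required before the walk and strength tests at a separate-day Post-Intervention visit or at the 3-Month visit

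*Combined protocol and SAP*

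**What the plan says.** Section 6.2.4 expects participants to be on neoadjuvant therapy during the study and gives this reason for looking at blood results: "These therapies may impact the participants circulating cytokines, thus rendering them ineligible to participate in physical activity". Staff look up the latest standard-of-care (SOC) labs before each PREHAB session. All three thresholds must be passed: neutrophils above 0.5 and platelets above 50 (both in 1000/uL), and hemoglobin above 8 g/dl. If one fails, the PI is told and "the participant will be unable to participate in the exercise session". Sessions resume when the values recover or when the PI allows it.

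Other places give the check the same scope. Section 5.3: "This study will review SOC labs undertaken closest to each PREHAB session to determine safe physical activity participation". Footnote 5 of the Time and Events Table (6.5): "SOC labs will be reviewed prior to each PREHAB session". Section 6.3.1 puts the stop-and-call instruction under Weeks 1 to 6. In the table, the row "SOC Lab Test Review" is marked at Baseline and Weeks 1 to 6 and is blank at Post-Intervention and 3 Months.

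The functional tests follow a different schedule. The 6-minute walk and the physical performance metrics are listed at Baseline (6.2.1), Post-Intervention (6.3.2) and 3 Months (6.4.1). Section 6.2.1 defines the strength part: "Strength is measured in reps within 60 seconds of leg press, bicep curls, heel raises, plank holds and lateral pull downs". The Post-Intervention visit falls "Within 14 days following the last PREHAB session", and it "Can be on the same day as the last PREHAB session". The same day is therefore allowed but not required.

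**The concern.** The stated reason for the check is fitness for physical activity in general, yet the written rule covers one setting for that activity. A leg press or lateral pull down is resistance work whether the appointment is called a session or an evaluation. As written, a participant whose counts bar a supervised session could be asked to do the 6-minute walk and the 60-second strength tests at an evaluation visit, and no rule would tell staff to look at the counts first.

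What is at stake is participant safety at two assessment visits, and a clear instruction for the staff who run them. The attendance endpoint and its decision rule are not involved.

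**Working it through.** The plan states no figure on this point, so the check sets the sections side by side.

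**1. Where the tests are run and where a count check applies**

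| Visit | Walk and strength tests | Lab review marked in 6.5 | Written rule that stops the tests on low counts |
|---|---|---|---|
| Baseline | Yes (6.2.1) | Yes | None: the 6.2.4 consequence names the exercise session only |
| Post-Intervention, same day as last session | Yes (6.3.2) | No, but the pre-session check that day covers it in practice | None for the tests themselves, but a failed check would already have barred that day's session |
| Post-Intervention, different day | Yes (6.3.2) | No | None |
| 3 Months | Yes (6.4.1) | No | None |

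The Baseline mark should not be read as full protection. The review is scheduled there, but no consequence is written for the tests.

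**2. Does the reason for the check end with the last session?** Nothing says so. Section 6.2.4 links the concern to therapy given during study participation. Section 5.4 puts participation at about 23 weeks, including 3 months of follow-up, and 4.1.1 admits any stage. The documents do not say how many participants will still be on such therapy at either later visit.

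**3. Does another clause supply a count check?**
- PAR-Q clearance (6.1.6) takes place at screening only.
- The symptom rule (5.2) is written for PREHAB exercise and acts once symptoms appear.
- Physician withdrawal (6.6.4) is discretionary.
- Record review for unanticipated problems (7.1) and the PI's continuous safety monitoring (9.5.1) run through follow-up, but neither names a count or a time point before testing.

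Each of these narrows the gap. None has a count trigger.

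**4. An illustration.** Suppose the final sessions are withheld for low counts. Assume also that the last PREHAB session in 6.3.2 means the last one attended, which the protocol does not define. The 14-day Post-Intervention window then runs while the participant is on hold, and no written rule extends the hold to the tests. The illustration needs that assumption. The gap in step 1 does not, because a separate-day visit has no required count check on any reading.

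**5. Workload of closing the gap.** Inputs: 16 participants (8.1), 3 sessions a week for 6 weeks (5.1.1), and two visits without a lab-review mark.
- Pre-session checks already scheduled: 16 × (3 × 6) = 16 × 18 = 288.
- Added checks, at most: 16 × 2 = 32. There are fewer where Post-Intervention is on the day of the last session.
- Ratio: 32 / 288 = 11.1%.

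Baseline adds nothing, because a review is already scheduled there. These figures describe effort. They say nothing about risk.

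**The case against.** The strongest reply is that the session-only scope may be deliberate. The thresholds were chosen by the study's own physiatrists and oncologists for up to 18 one-hour sessions with resistance near 75% of the one-repetition maximum (5.2). A single assessment visit is a different exposure. The PI already knows of any hold, reviews records through the 3-Month visit and can intervene. Withholding tests from the sickest participants also makes exploratory data selectively missing in a trial of 16.

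Part of this stands. A deliberate exemption is possible, and one sentence of justification would settle the matter, but the protocol does not give it. The cost in missing data is real and has to be managed. The PI's involvement makes the worst case less likely without putting a count check before the tests.

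A reader might also infer more than the text supports:
- *The tests would be done with nobody having looked at the chart.* Sections 7.1 and 9.5.1 provide for record review. What is missing is a required count check.
- *All the strength tests are loaded.* Section 6.2.1 gives repetitions and states no load. Leg press, curls and pull downs are resistance exercises, but heel raises and plank holds need no added weight.
- *The protocol contradicts itself.* It does not. The rule is consistent in every section and is narrower than its stated reason.
- *Home exercise should stop by default during a hold.* The documents do not require this. A failed threshold already prompts a call to the PI, and 5.1.3 does not treat missed home minutes as a deviation.

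**Conclusion.** The point holds as a gap in scope, and closing it is a cheap safety improvement. The thresholds in 6.2.4 act only before supervised sessions. Nothing requires a count check before the 6-minute walk and 60-second strength tests at a separate-day Post-Intervention visit or at 3 Months. At Baseline the review is scheduled without a consequence for the tests.

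The size in terms of harm is unknown. The documents report neither how often counts fall below the thresholds nor how often sessions are held, and no risk figure should be inferred. The conclusion rests on reading the rule as written and on taking the blank table cells to mean that no review is scheduled. Sections 6.3.2 and 6.4.1 agree with that reading, since neither lists a review. The primary endpoint and its analysis are unaffected.

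**What to change.** 1. In the Time and Events Table, mark the lab-review row at Post-Intervention (when not on the day of the last session) and at 3 Months. List the review in 6.3.2 and 6.4.1.
2. Add to 6.2.4, in words such as: *Before the 6-minute walk and the 60-second strength tests at any visit, staff check the most recent SOC result and record its date. If a threshold is not met, staff call the PI and either defer these tests within the visit window or proceed at the PI's discretion.*
3. For any test missed for this reason, record *withheld for low counts*. Section 5.6 ties exploratory evaluability to completing the 3-Month visit, so the reason for a missing test should be visible in the data.

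Weight and questionnaires go ahead as planned.

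**Cost:** two table marks, two list entries, a few sentences and at most 32 chart checks across the trial. No new blood draws are needed, because existing SOC results are used.

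**Downside:** a few exploratory walk and strength results may be delayed or missing, mainly in sicker participants, so a summary of observed values could look too favorable. Reporting the number withheld beside each summary makes this visible. SOC results may also be old by 3 Months, so the added protection there rests partly on the PI's judgement.

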6.2.5 Fitbit Training and Use

- Training will include how to wear, charge and sync Fitbit
- Participants will start wearing the Fitbit continuously from the Baseline session
- Subjects who are unable to meet eligibility criteria 4.1.9 or who do meet exclusion criteria 4.2.3 will be exempt from this study task.

6.2.6 Dietitian Referral

- Patients not previously referred to a hospital dietitian during their pancreatic cancer care will be referred

6.2.7 Online Pain Portal Training (first 8 participants only)

- Training will include how to use and interact with the validated online portal (www.painguide.com) created by the University of Michigan. The exercise physiologist/personal trainer staff will follow up with patients weekly to biweekly to record usage of the portal.
- Subjects who are unable to meet eligibility criteria 4.1.9 will be exempt from this study task.

6.3 Study Procedures**6.3.1 Week 1 – Week 6* (Within 14 days of Baseline)**

- 3 x weekly 1 hour PREHAB session
- Continuous activity monitoring (Fitbit)
- Unanticipated Problem review
- Optional use of the Online Pain Portal. Self-Report portal interaction.
- SOC Lab review – **If labs do not meet criteria in Section 6.2.4, STOP and call the PI**
- 150 minutes of self-managed exercise per week at home (measured by Fitbit data)

*Up to 3 missed sessions will be made up in a 7th week

6.3.2 Post-Intervention Evaluation (Within 14 days following the last PREHAB session)

Can be on the same day as the last PREHAB session

- Vitals (Weight, BMI)
- Six-minute walk test
- Hand grip strength
- Physical performance metrics
- Short performance physical battery
- Unanticipated Problem review
- PROMIS-29 (for non-English speaking patients, an interpreter will be used for the questionnaire)
- PROMIS Cancer 3D Function Profile (for non-English speaking patients, an interpreter will be used for the questionnaire)
- Patient Global Impression of Change (Only those participants who used the Online Pain portal)
- Continuous activity monitoring (Fitbit)

6.4 Follow-up Procedures - Three Month Follow-Up (\pm 14 days)**6.4.1 Physical Evaluation**

- Vitals (Weight, BMI)
- Six-minute walk test
- Hand grip strength
- Physical performance metrics
- Short performance physical battery
- Unanticipated Problem review
- Last day of Fitbit Use

6.4.2 Questionnaires

- PROMIS-29
- PROMIS Cancer 3D Function Profile

For non-English speaking patients, an interpreter will be used for the questionnaires.

6.4.3 SOC Abdomen CT scan

- Document date of closest SOC Abdomen CT scan (ok if occurs outside of the 3 month \pm 14 days window)

6.4.4 Healthcare Utilization Assessment (May be assessed by chart review, in-person discussion at visit and/or phone call)

- Number of hospitalizations
- Reason for hospitalization
- Days hospitalized
- Disposition: continued therapy, hospice, death, other
- If underwent resection then evaluate post-op complications - Post-operative complications will be assessed using the Clavien-Dindo classification system^{17,18}

6.5 Time and Events Table

	Screening (Within 28 days of Baseline)	Baseline (Within 14 days of first PREHAB session)	Week 1 – Week 6¹	Post-Intervention Evaluation (Within 14 days of last PREHAB session)	3 Month Follow-Up (± 14 days)
Informed Consent	X				
Confirm Eligibility	X				
Medical History	X				
Demographics	X				
Pregnancy status ²	X				
Godin Leisure-Time Exercise Questionnaire	X				
PAR-Q	X				
Physical Activity Assessment	X				
Vitals (Height, Weight, BMI) ³		X		X	X
Six Minute Walk Test		X		X	X
Hand Grip Strength		X		X	X
Physical Performance Metrics		X		X	X
Short Performance Physical Battery		X		X	X
Unanticipated Problem review			X	X	X
PROMIS-29		X		X	X
PROMIS Cancer 3D Function Profile		X		X	X
SOC Abdomen CT Scan ⁴		X			X
SOC Lab Test Review		X	X ⁵		
Fitbit activity monitoring ⁶		X	X	X	X
Dietitian referral ⁷		X			
Online Pain platform ⁸ Training		X			
Online Pain platform use ⁸			X		
Online Pain platform compliance			X ⁹		
3 x Weekly 1HR PREHAB session			X		
Patient Global Impression of Change ¹⁰				X	
Healthcare Utilization Assessment					X

BMI: Body Mass Index, CT: Computed Tomography, PAR-Q: Physical Activity Readiness Questionnaire

1. Up to 3 missed sessions will be made up in a 7th week
2. Pregnancy status confirmed with patient and via medical record review

3. Height will only be collected at Baseline
4. CT scans completed closest to baseline and 3-month follow-up will be used, even if they occurred outside of the relevant visit window.
5. SOC labs will be reviewed prior to each PREHAB session
6. Fitbit use is only required by those who met eligibility criteria 4.1.9 and do not meet exclusion criteria 4.2.3.
7. Only patients not previously referred to a Dietitian will be referred by the study team
8. Online Pain platform training and use is only required for those who met eligibility criteria 4.1.9 (First 8 participants only)
9. Online Pain platform compliance will be self-reported every 2 weeks (First 8 participants only)
10. Only completed by the participants who used the Online Pain Portal

6.6 Removal of Subjects from Study

Patients can be taken off the study intervention and/or study at any time at their own request, or they may be withdrawn at the discretion of the investigator for safety, behavioral or administrative reasons. The reason(s) for discontinuation will be documented and may include:

- 6.6.1** Patient voluntarily withdraws (follow-up permitted);
- 6.6.2** Patient withdraws consent (termination of treatment and follow-up);
- 6.6.3** Patient is unable to comply with protocol requirements;
- 6.6.4** Treating physician determines continuation on the study would not be in the patient's best interest;
- 6.6.5** Patient becomes pregnant (pregnancy to be reported along same timelines as a serious adverse event);
- 6.6.6** Lost to follow-up. If a research subject cannot be located to attend their 3-month follow up session subject may be considered "lost to follow-up." All attempts to contact the subject during the 3 months must be documented.
- 6.6.7** Patient displays aggression or hostility towards study staff.

7.0 UNANTICIPATED PROBLEMS INVOLVING RISK TO SUBJECTS OR OTHERS (UPIRSO)

7.1 UPIRSO Collection and Reporting

As this trial intervention and the corresponding research procedures pose no known risk to subjects, unexpected/unanticipated problems will be reported in place of Adverse Event reporting. Treating investigator or PI will evaluate patients through medical record review or patient visit from PREHAB session 1 through to the 3 Month Follow-Up visit for any unanticipated problems.

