2.4.2 Secondary Efficacy Endpoint

Safety - PREHAB program safety will be evaluated by monitoring unanticipated problems involving risk to subjects or others (UPIRSO). At each PREHAB session, the post intervention evaluation and the 3 month follow up visit the exercise physiologist or personal trainer will record any side effects or symptoms reported by the subject. Within a week the treating physician or Principal Investigator (PI) will review and classify all events. Any events meeting the definition of a UPIRSO will be documented on the UPIRSO log and/or to the IRB by the coordinator within 10 business days.

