5.2 PREHAB intensity / injury

Patients will participate in specific PREHAB exercises as they are able. Aerobic activity will be adjusted per participant to a level of 4-6 on a modified Borg Scale. Level of resistance for each exercise will be adjusted by the exercise trainer/physiologist such that repetitions are being performed at ~75% of the one repetition maximum. Chest specific exercises including chest press, dips, and push-ups will be omitted for patients with ports. Any patients experiencing symptoms of dizziness, lightheadedness or dyspnea will be instructed to take a break until symptoms resolve. Patients with unresolving symptoms or more serious symptoms like chest pain will be referred to the cancer rehabilitation physician who will evaluate the patient and refer to acute services as indicated.

Patients who sustain injuries related to the PREHAB sessions may remain on the study as long as their injury does not prevent them from completing the exercise protocol.

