5.6 Subject Replacement

Subjects who withdraw from the study prior to their PREHAB session 1 will be replaced.

Subjects who attend at least the first session will be evaluable for both the primary and secondary endpoint analysis. To be evaluable for exploratory endpoints subjects will need to complete the 3 month follow up visit.

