7.1.1 Unanticipated Problem Involving Risk to Subjects or Others (UPIRSO)

Unanticipated problems include any incident, experience, or outcome that meets all of the following criteria:

- Unexpected (in terms of nature, severity, frequency) given (a) the research procedures that are described in the protocol-related documents, such as the Institutional Review Board (IRB) approved

- research protocol and informed consent document; and (b) the characteristics of the subject population being studied;
- Related or possibly related to participation in the research (possibly related means there is a reasonable possibility that the incident, experience, or outcome may have been caused by the procedures involved in the research); and
- Suggests that the research places subjects or others at a greater risk of harm (including physical, psychological, economic, or social harm) than was previously known to an individual or group of individuals (including research subjects, research staff, or others not directly involved in the research).

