8.3.1 Safety Analysis

All subjects entered into the study at Baseline will be included in the safety analysis. The frequencies of UPIRSOs by type, body system, severity and relationship to study intervention will be summarized.

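### Safety is analysed only as UPIRSOs, so foreseen exercise symptoms and injuries are recorded but not summarised, and the safety population is defined in three ways

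*Combined protocol and SAP*

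**What the plan says.** Section 2.2.1 sets one secondary objective, the safety of the 6-week program, and 2.4.2 measures it by monitoring UPIRSOs. Section 7.1 gives the reason, that the intervention and procedures carry no known risk, and concludes that "unexpected/unanticipated problems will be reported in place of Adverse Event reporting". Section 7.1.1 defines the term: "Unanticipated problems include any incident, experience, or outcome that meets all of the following criteria". The three criteria are unexpectedness (in nature, severity or frequency), a related or possibly related link to research participation, and a suggestion of greater risk than previously known.

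The planned analysis in 8.3.1 is: "The frequencies of UPIRSOs by type, body system, severity and relationship to study intervention will be summarized".

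Collection is wider than analysis. Under 2.4.2, at each session, the post-intervention evaluation and the 3-month visit, the exercise physiologist or trainer "will record any side effects or symptoms reported by the subject", and a physician classifies all events within a week. Section 5.2 foresees dizziness, lightheadedness, dyspnea, chest pain and training injuries; of the last it says "Patients who sustain injuries related to the PREHAB sessions may remain on the study", provided they can still complete the exercise protocol.

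On who is analysed, 8.3.1 says "All subjects entered into the study at Baseline will be included in the safety analysis", while 5.6 says "Subjects who attend at least the first session will be evaluable for both the primary and secondary endpoint analysis". Section 8.2 limits the analysed data to eligible subjects with at least 60% session participation and states no exception for safety.

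**The concern.** A UPIRSO is a regulatory reporting category. It picks out events that change what is known about the risk of the research. The safety objective asks a different question: how often does this program cause symptoms or injuries in patients with pancreatic cancer? An event can be caused by training, matter to the patient and interrupt the program, and still fail the UPIRSO definition because it was foreseen. If only UPIRSOs are tabulated, the trial can follow its plan exactly and leave that question unanswered, although the records needed to answer it will exist. A reader of the report could take a short or empty UPIRSO table as evidence of safety.

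The choice of population adds to this. Patients who stop because of an injury are those a safety summary most needs to keep, and an attendance-based analysis set can remove them.

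**Working it through.** The plan states no safety figure or event rate, so there is nothing to reproduce. The check sets the sections side by side and then shows what a zero count could and could not mean.

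**1. Path of a foreseen event.** Take a training injury of a kind covered by 5.2, at expected severity and frequency.
- 2.4.2: recorded at the session and classified within a week.
- 7.1.1: fails the unexpectedness criterion, so it is not a UPIRSO, even if training caused it.
- 2.4.2: not required on the UPIRSO log.
- 8.3.1: not tabulated.
- 8.3: the general promise of descriptive measures for secondary endpoints does not reach it, because the endpoint in 2.4.2 is UPIRSO monitoring.

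**2. What zero would mean.** With n = 16 and no UPIRSO, the exact one-sided 95% upper bound is 1 − 0.05^(1/16) = 0.171, or 17.1%. It bounds the proportion of patients with a UPIRSO. It places no bound on symptoms or injuries.

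**3. How likely zero is (assumed rates).** Let q be the share of patients with an exercise-related event and u the share of those whose event meets the UPIRSO definition. Both are assumptions. With independent patients, P(no UPIRSO) = (1 − q·u)^16.

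| q | u | Expected patients with an event, 16q | Expected UPIRSO patients, 16qu | P(no UPIRSO) |
|---|---|---|---|---|
| 0.10 | 0.05 | 1.6 | 0.08 | 0.995^16 = 92% |
| 0.30 | 0.05 | 4.8 | 0.24 | 0.985^16 = 79% |
| 0.30 | 0.10 | 4.8 | 0.48 | 0.97^16 = 61% |
| 0.30 | 0.25 | 4.8 | 1.2 | 0.925^16 = 29% |
| 0.50 | 0.25 | 8.0 | 2.0 | 0.875^16 = 12% |

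If all exercise-related events were counted, P(at least one) = 1 − (1 − q)^16, which is 81% at q = 0.10 and 99.7% at q = 0.30.

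**4. Population.** Three rules apply to the same endpoint.
- 8.3.1: everyone entered at Baseline. This includes anyone who leaves before session 1, who is replaced under 5.6 and for whom no event review is scheduled.
- 5.6: those who attend session 1.
- 8.2, read literally: those with at least 60% of sessions. The program has 3 × 6 = 18 sessions and 0.60 × 18 = 10.8, so 11 are needed. A patient who stops for injury after 10 or fewer would be left out.

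**5. Observation window.** Section 7.1 starts event review at session 1, and the Time and Events Table (6.5) shows no unanticipated-problem review at Baseline. The Baseline visit nevertheless includes the six-minute walk and 60-second strength tests (6.2.1).

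**The case against.** The strongest defence starts from 7.1.1. Unexpectedness is judged on severity and frequency as well as nature, so an unusually severe or unusually frequent injury of a foreseen kind can qualify. That is correct. A reader might infer that foreseen events can never be counted, or that the definition itself forces the result close to zero. The text does not support either reading; it makes a low count likely, no more.

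Nor does 5.2 settle what is expected. It gives handling instructions, not a list of expected events, and 7.1.1 also refers to the consent document, which was not available here. Given the no-known-risk statement in 7.1, a classifier could treat a training injury as new risk. This stands as a limit on certainty. It also shows that 5.2 and 7.1 leave classification open.

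A reader might think the breakdown by relationship in 8.3.1 is empty, since every UPIRSO is already related. It is not: the definition concerns research participation, the table concerns the study intervention, and an event during a walk test could differ on the two. A reader might also infer a failure to collect data at sessions; 2.4.2 shows otherwise.

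On populations, the specific rule in 8.3.1 would normally prevail over the general one in 8.2, and the gap between 8.3.1 and 5.6 affects only people who leave between Baseline and session 1. Both points are fair, but 8.2 names no exception and 5.6 still disagrees with 8.3.1.

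Finally, UPIRSO-only reporting may suit a study handled as minimal risk. That justifies a reporting route to the IRB. It does not make the UPIRSO count a measure of program safety.

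**Conclusion.** The point holds as a gap in endpoint definition and analysis. Events that the protocol foresees, at expected severity and frequency, are recorded and classified but not summarised, so the only secondary objective cannot be answered by the planned table. Its size cannot be derived from the documents. Under the assumed rates above, the chance of an empty UPIRSO table runs from 12% to 92%, which supports likely but not certain. The 17.1% bound for 0 of 16 describes UPIRSOs alone and does not measure the gap.

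The conflict between the three population rules is plain on the text. Its effect is small between 8.3.1 and 5.6, and potentially larger if 8.2 were applied to safety, because exclusion could then depend on the outcome. The conclusion assumes that no analysis of other recorded events is set out in material not seen, namely the consent document and the part of section 7 between 7.1.1 and 7.2.2. The change should be made; it does not affect the primary feasibility test.

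**What to change.** - **8.3.1, analysis:** add a descriptive summary of all side effects, symptoms and injuries recorded under 2.4.2. Give patients with at least one event and events per session delivered, by type, severity and relation to exercise. Show UPIRSOs as a subset.
- **Population:** state in 8.3.1 that the safety population is all subjects with at least one session, regardless of later attendance, consistent with 5.6. Exempt safety explicitly from 8.2.
- **Baseline:** record events at the Baseline physical tests, add this to 6.5 and 7.1, and list these events separately from the session-based rates.
- **Consistency:** reconcile the no-known-risk statement in 7.1 with the symptoms and injuries foreseen in 5.2.

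UPIRSO reporting to the IRB and the DSMC need not change.

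**Cost:** 2.4.2 has all events classified but names no severity scale or relatedness categories for non-UPIRSO events, so those fields and definitions must be added, together with one table, one Baseline check and a protocol amendment. The safety figures will also look less favourable than a UPIRSO count alone.
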